People who live with HIV (PLWH) experience a high incidence of neurocognitive deficits and HIV-associated non-AIDS (HANA) disorders, including cardiovascular disease (CVD), metabolic dysfunction, and autonomic decline. While antiretroviral treatment (ART) has reduced AIDS-related morbidity, both the virus and the medications are associated with lipid disorders that also increase CVD risk, including dyslipidemia and lipodystrophy. Consequently, the development of effective lifestyle interventions to reduce the incidence of HIV-associated neurocognitive disorders (HAND) and decrease metabolic disorders is a high priority. Physical activity (PA) has been utilized as an effective tool to improve health in PLWH, but may not be sufficient by itself to improve lipid levels. Existing PA interventions in PLWH typically required strenuous PA and significant resources that limit feasibility for many people living with the disease. Recent work indicates that interrupting periods of sedentary behavior (SB), independent of PA, also has a significant beneficial effect on metabolic function, but SB has not been well-studied in PWLH. Mediterranean-style diets (MedDiet) are also effective at improving CVD risk factors in HIV-uninfected individuals and are reported to reduce cognitive decline in persons at risk for Alzheimer's disease, but have not been widely tested in PWLH. We recently developed a novel and personalized Short Message Service (SMS) mobile phone text messaging intervention (iSTEP) that is designed to increase moderate PA in PLWH. Our objective is to expand upon this work and conduct an RCT examining the efficacy of iSTEP in combination with a mobile mHealth MedDiet intervention tailored to PLWH. 150 PLWH will be randomly assigned to a control group ($n = 50$), a 6-month iSTEP group with just a PA/SB intervention ($n = 50$), or a 6-month intervention with both PA/SB and MedDiet components ($n = 50$), where participants receive daily interactive SMS/MMS messages designed to increase moderate PA, reduce SB, and promote adherence to a MedDiet, including walnut consumption. PA/SB will be quantified by accelerometer, Fitbit step counts, and self-report, while MedDiet adherence will be assessed by self-report (Diet History Questionnaire and weekly SMS feedback) and also objective measures (polyunsaturated fatty acid levels - PUFA in blood). We will also conduct a follow-up assessment 6 months after the end of the intervention (accelerometer, neurocognitive testing, PUFA levels) to assess PA and MedDiet adherence. We hypothesize that iSTEP (both intervention arms) will increase PA, reduce SB, and improve neurocognition compared to control; the iSTEP + MedDiet group will demonstrate improvement in CVD risk factors and neurocognition compared to the PA intervention alone. Findings from this proposal will lay the groundwork for development of novel large-scale mobile PA/diet interventions dedicated to treating HAND and improving cardiovascular health for PLWH.

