mHealth interventions improve PA and diet. Mobile health (mHealth) text messaging interventions have promoted a variety of health behaviors, including increasing PA and reducing body fat and cholesterol over periods as short as 12 weeks^{88 89-91}. Although Short Message Service (SMS) protocols have been developed to improve medication adherence in PLWH^{92, 93}, this methodology has not been utilized to promote PA or diet interventions in this population. In addition, few studies have specifically targeted SB in PLWH⁹⁴. Participant feedback has focused on three themes: adding a competitive component to iSTEP (allowing participants to compare their PA with others), being able to track their SB, not just steps, and the inclusion of diet as part of the intervention. Here we propose to conduct an mHealth intervention that examines the efficacy of a PA/SB intervention alone compared to PA/SB + MedDiet condition designed to improve neurocognitive performance and reduce CVD risk in PWLH with HAND and metabolic syndrome.

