5.0 STATISTICAL ANALYSIS PLAN

5.1. Analyses.

For all analyses, two-sided tests with significance level $\alpha=0.05$ will be used. Where necessary, assumptions for parametric testing will be checked prior to analyses. If assumption of normal distribution is not met, variable transformation (e.g., log) or nonparametric methods will be used. Randomization scheme should insure comparability of the groups on demographic and medical characteristics. Baseline characteristics will be compared between the groups using ANOVA for numeric values (e.g., age) and chi-square test for categorical variables (e.g., gender). Baseline characteristics found to be different between the groups will be used as covariates in the primary analyses to control for possible effect of group differences on the outcomes. For the primary analysis, PA outcomes will be measured at 2 visits (baseline (BL) and 24 weeks) with the exception of accelerometer and 7DPAR data, which will be measured at 3 visits (BL, 24 weeks, and 48 weeks); cognition and cardiovascular risk factors will also be assessed at 3 visits. Mixed models analyses will be conducted with a) the inclusion of all available data, assuming values missing at random; b) the baseline carry forward (BOCF) imputation method; and c) including only the participants who complete the study. For Hypothesis 1.1, changes in numeric outcomes measuring PA (e.g., time spent on PA, time spent on sedentary behavior) from baseline to week 24 (to week 48 for accelerometer/7DPAR measures) will be compared between the iSTEP and control groups using mixed effects models with subject-specific random effect. Subject-specific random effects will estimate individual changes in outcomes (slopes) as well as individual baseline values (intercept) to take into account natural variability in measured values between subjects. The models will regress PA measures on group (iSTEP vs. control), time (2 time points), and their interaction. A significant interaction term ($p<0.05$) would indicate a significant treatment effect or, in other words, significant differences in mean changes in outcomes over time (slopes) between the two treatment groups. Mixed effects model with terms for group, time (3 visits), and their interaction will be used to evaluate effect of iSTEP intervention on changes in accelerometer values. In explorative analysis, we will compare daily

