changes in PA variables measured daily (step count, time spent in PA, and time in SB) between iSTEP and control groups using similar method as above, except using many time points (days) instead of just 2 or 3. For Hypothesis 1.2, Global Mean T-score will measure cognitive performance at all visits; practice effect correction will be applied to values measured at the 24 and 48 weeks. Again, mixed effects model with subject-specific random effect will be used to regress T-score on group (iSTEP vs. control), time (3 time points), and their interaction. We hypothesize that a significant interaction term will show that the slope representing an improvement in cognition will be the smallest for the control group and the largest for the iSTEP group. Similarly, for Hypothesis 2.1, changes in multiple numeric outcomes related to cardiovascular disease risk factors (e.g., cholesterol) will be evaluated with separate mixed effects models. The models will regress the outcomes on group (control, iSTEP PA/SB, iSTEP PA/SB + MedDiet), time (3 time points), and their interaction, including subject specific random effect. We hypothesize that a significant interaction will be observed and that it will show greater improvements in the outcomes for iSTEP groups, with iSTEP PA + MedDiet group having the best results. Similar approach will be used for Hypothesis 2.2, were changes (slopes) in Global Mean T-scores will be compared between the iSTEP PA/SB + MedDiet and iSTEP PA/SB groups and between the iSTEP PA + MedDiet group and controls. Additional analyses: We will conduct exploratory analyses using mixed models to assess changes in diet markers (omega-3, DHA, EPA, percent fat intake on the DHQ) over time to assess if there are group differences and if these markers predict CVD/NP outcome. Multiple regression analyses will be conducted across all participants to examine which factors (PA amount, SB change, MedDiet Score) significantly predict NP and CVD risk factors, including metabolic measures and inflammatory markers at the 6-month and 12-month visits. We will collect Likert scale data that identify what aspect of iSTEP is most useful (e.g., step self-monitoring, step count goals, types of PA/SB messages, comparing PA data to other PLWH) and conduct regression analyses to identify factors (e.g., PA barriers, SMS adherence) that best predict study outcome and PA/diet maintenance.

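### For Hypothesis 2.1, section 5.1 states only a three-group interaction, which does not test whether diet adds to physical activity and is out of line with 5.2 and the study question

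*Combined protocol and SAP*

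**What the plan says.** The protocol's opening summary states the hypothesis as a comparison of two arms: "the iSTEP + MedDiet group will demonstrate improvement in CVD risk factors and neurocognition compared to the PA intervention alone". The Introduction (1.0) says the study "examines the efficacy of a PA/SB intervention alone compared to PA/SB + MedDiet condition designed to improve neurocognitive performance and reduce CVD risk".

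Section 5.1 first explains, for Hypothesis 1.1, that a significant group-by-time interaction indicates a treatment effect, meaning "significant differences in mean changes in outcomes over time (slopes) between the two treatment groups". It then turns to the cardiovascular outcomes: "Similarly, for Hypothesis 2.1, changes in multiple numeric outcomes related to cardiovascular disease risk factors" are to be analysed in separate mixed models. "The models will regress the outcomes on group (control, iSTEP PA/SB, iSTEP PA/SB + MedDiet), time (3 time points), and their interaction". The expected result follows: "We hypothesize that a significant interaction will be observed and that it will show greater improvements in the outcomes for iSTEP groups", with the combined arm expected to do best. No pairwise contrast is named for Hypothesis 2.1.

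The next sentence does name contrasts, but for Hypothesis 2.2 and cognition: "changes (slopes) in Global Mean T-scores will be compared between the iSTEP PA/SB + MedDiet and iSTEP PA/SB groups", and also the combined arm against control.

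Section 5.2 states power for the three-visit models, Hypothesis 2.1 included, in terms of differences between any two arms. The Figure 1b caption lists cardiovascular risk factors among the outcomes for which the combined arm is compared with either other arm, from baseline to 48 weeks.

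**The concern.** With two groups, a significant group-by-time interaction is a comparison of those two arms, so the reading given for Hypothesis 1.1 is correct. Hypothesis 2.1 carries the same approach to three groups, where that reading no longer holds. A three-group interaction says that the arms do not all change alike. It does not say which arms differ, and it is significant with high probability when both active arms improve equally over control and diet contributes nothing.

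At stake is the trial's answer on diet and cardiovascular risk. If the interaction is the only stated test, a significant result with the combined arm numerically ahead could be reported as support for an added diet effect that the data do not show. Conversely, a real diet effect would have no designated test.

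**Working it through.** **Inputs from the documents.** 50 randomised per arm (opening summary); 20% dropout, leaving 40 per arm (5.2); two-sided 0.05 (5.1); at least 80% power for a large effect between two arms in the three-visit models (5.2).

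**Assumptions.** Effects are in SD units of the change score, so SD = 1. The text gives no numeric d or intra-class correlation, and Figure 1 is not shown, so d is varied. Large is taken as 0.8. All rates are per outcome.

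**The plan's own figures.** 50 × 0.8 = 40 per arm. For two arms of 40, a t-test has 80% power at a difference of 0.634 and 94% at 0.8. The statement in 5.2 therefore reproduces for a pairwise comparison.

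**Interaction when diet adds nothing.** Take mean changes (0, d, d) for control, PA/SB and PA/SB + MedDiet. The test is F on (2, 117) degrees of freedom, critical value 3.07, with noncentrality

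λ = 40 × Σ(μᵢ − μ̄)² = 40 × (2/3)d² = 26.67d².

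For d = 0.4, λ = 4.27; for d = 0.8, λ = 17.07. The ranked-first column comes from simulation with 400,000 trials per d.

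| d | Interaction significant | Significant and combined arm numerically first |
|---|---|---|
| 0 | 5% | 1.6% |
| 0.1 | 7% | 3.3% |
| 0.2 | 14% | 7% |
| 0.4 | 43% | 21% |
| 0.5 | 62% | 31% |
| 0.8 | 96% | 48% |

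The contrast of the combined arm with PA/SB, used alone, falsely favours diet in 2.5% of trials at every d.

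**Dependence on how time is modelled.** With linear time and equally spaced, complete visits, the slope is (week 48 − baseline)/2. If the effect halves by week 48, the row for d/2 applies: 7% instead of 21% ranked first for d = 0.4, and 21% instead of 48% for d = 0.8. With categorical time (4 df, assumed correlation 0.5 between the two changes, ranked at week 24), the same fading gives 17% and 46%.

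**Power of the two tests when diet does add something.** The contrast has noncentrality δ/√(2/40) = 4.472δ.

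- True changes 0, 0.4, 0.8: interaction λ = 40 × 0.32 = 12.8, power 90%. Contrast 4.472 × 0.4 = 1.79, power 43%.
- True changes 0, 0, 0.634: interaction λ = 26.67 × 0.634² = 10.7, power 83%. Contrast 4.472 × 0.634 = 2.84, power 80%.

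In the first case most of the interaction's power comes from physical activity rather than diet.

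**The case against.** The strongest reply is that the same statistical section already contains the comparison. The Figure 1b caption gives both contrasts for the combined arm, names cardiovascular risk factors, and gives a span from baseline to 48 weeks. Hypothesis 2.2 is introduced as following a similar approach and spells out the same contrasts, and 5.1 uses slope language throughout, so a slope over three visits can be inferred. The likely intent is an interaction followed by pairwise comparisons. This stands, and it limits the point: a reader might infer that the plan has no diet comparison or time span for these outcomes anywhere, and the documents do not support that. What remains is that a power caption does not say which test answers Hypothesis 2.1, and that Hypothesis 2.2's contrasts are stated for T-scores only.

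A reader might also infer that the plan will claim a diet benefit whenever the interaction is significant and the combined arm ranks first. The documents do not say so: the sentence is an expectation, not a claim rule. In the scenario tabulated above, a significant interaction would also be correct for the first half of that expectation, that the iSTEP arms improve more than control. Only the ranking would mislead.

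Finally, the summary and Introduction doubt that physical activity alone improves lipids. If it does nothing (d = 0), the ranked-first rate is 1.6%, below the contrast's own 2.5%. This too is fair, and it is why the range starts at zero. It does not cover the other risk factors, and Hypothesis 2.1 itself expects both iSTEP arms to improve.

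**Conclusion.** The point holds as a mismatch within the plan. The only test that 5.1 states for Hypothesis 2.1 does not test the cardiovascular hypothesis in the opening summary, and it does not match the pairwise comparisons on which 5.2 bases power. With no diet effect, the interaction is significant in 5% to 96% of trials as the assumed common effect of the active arms runs from 0 to 0.8 SD.

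The ranked-first rates of 1.6% to 48% are not an error rate of the plan as written. They apply only if best is read as a rank, and rates above 20% need a physical-activity effect of about 0.4 SD or more. The low end fits the protocol's own doubt about lipids. All these figures rest on 40 per arm, change scores with SD 1 and an assumed d. The reasoning that the interaction cannot isolate the diet effect does not depend on d. This should be fixed before analysis; it does not call the design or the sample size into question.

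**What to change.** In 5.1, state that for each cardiovascular risk factor the diet part of Hypothesis 2.1 is tested by the difference in change between iSTEP PA/SB + MedDiet and iSTEP PA/SB, estimated from the planned three-arm mixed model. Give the span: baseline to 48 weeks if the Figure 1b span is intended, or baseline to week 24 if the end of the intervention is intended. Make 5.1 and 5.2 agree on it.

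Also report PA/SB + MedDiet against control, and PA/SB against control. The latter is needed because Hypothesis 2.1 expects both iSTEP arms to improve, so copying Hypothesis 2.2's two contrasts would not be enough. Treat the three-group interaction as a global test only. Requiring it to be significant first would cost power for the diet contrast: 53% instead of 60% for true changes 0, 0, 0.5.

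The edit is short but requires a decision on the time span. Sample size, data and model do not change. The price is fewer positive diet claims when physical activity itself works (43% against 90% power for true changes 0, 0.4, 0.8), because the higher figure answers a different question. When physical activity alone does nothing, little is lost (80% against 83% for 0, 0, 0.634).

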5.2 Power Analysis

For all power calculations 20% dropout rate is assumed based on prior mHealth diet interventions¹¹⁹, leaving N=40 for each of the three groups.

For mixed effects models comparing change in outcomes over time between groups, estimates of power depend on intra-class correlation (within-subject correlation of outcomes measured at different times) and number of total visits, including baseline. For models based on 2 visits (hypothesis 1.1, except accelerometer), there will be at least 80% power to detect a medium to large effect size, Cohen's d , for the difference in mean change in outcomes from baseline to week 24 visit (Fig 1a). For models based on 3 visits (accelerometer /7DPAR values in hypothesis 1.1; hypotheses 1.2 through 2.2), there will be at least 80% power to detect a large effect size, d , for mean differences in outcome changes over three visits between any of the two groups (Fig 1b).

[figure not shown]

Figure 1a. Comparing changes in PA outcomes between iSTEP group ($n = 40$ after 20% dropout) and controls ($n = 40$ after 20% dropout) from BL to week 24. **Figure 1b.** Comparing changes in accelerometer data, cardiovascular disease risk factors, or cognitive outcomes between iSTEP PA+MedDiet and either of the other two groups ($n = 40$ for each group after 20% dropout) from BL to 48 weeks.

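### The exploratory pooled regressions of 6- and 12-month outcomes on PA, SB change and MedDiet Score do not specify the baseline outcome, so pre-existing differences can appear as behavioural predictors.

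*Combined protocol and SAP*

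**What the plan says.** The regressions appear in one sentence of Section 5.1, under additional analyses: "Multiple regression analyses will be conducted across all participants to examine which factors (PA amount, SB change, MedDiet Score) significantly predict" followed by "NP and CVD risk factors, including metabolic measures and inflammatory markers at the 6-month and 12-month visits". They pool the three arms, name three factors of interest, and write the outcome as a value at a visit. Neither the baseline outcome nor randomised arm is mentioned.

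Two other parts of Section 5.1 bear on this:

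- The only general covariate rule is "Baseline characteristics found to be different between the groups will be used as covariates in the primary analyses". It covers primary analyses, and only characteristics on which the groups differ.
- The models for the numbered hypotheses do list their terms. For Hypothesis 2.1: "The models will regress the outcomes on group (control, iSTEP PA/SB, iSTEP PA/SB + MedDiet), time (3 time points), and their interaction", plus a subject-specific random effect.

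Section 5.1 also states that "two-sided tests with significance level $\alpha=0.05$ will be used" for all analyses.

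**The concern.** A follow-up level carries the baseline level with it, and so does a person's activity. If people who are more active at entry also have better lipids or cognition at entry, the two follow-up measurements are correlated even when changing activity does nothing. A regression without the baseline outcome cannot separate this from a behaviour effect.

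The Introduction relates the amount of sitting to metabolic health and walking to lipids, so a zero baseline correlation would sit oddly with the study's rationale. The documents give no value, however.

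Arm raises a separate issue. Only one arm receives the diet component, so MedDiet Score is tied to assignment, and its coefficient can absorb other effects of being in that arm.

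At stake is the reading of an exploratory result about which behaviours go with better outcomes, in a study meant to prepare larger PA and diet interventions.

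**Working it through.** **Inputs from the documents.** 50 participants are randomised per arm. Section 5.2 says "For all power calculations 20% dropout rate is assumed". Then 50 × (1 − 0.20) = 40 per arm, which reproduces the plan's figure, and 3 × 40 = 120 in a pooled regression. Alpha is 0.05, two-sided. The plan states no power or error figure for these regressions.

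**Assumptions, none given in the documents.** r is the baseline correlation between PA and the outcome, taken from 0 to 0.3. The correlation between baseline and follow-up is t_PA for PA and t_Y for the outcome, each 0.6 to 0.8. Behaviour has no effect on the outcome.

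**Hand approximation for PA amount as the only predictor.** The follow-up correlation is c = r × t_PA × t_Y. With z = atanh(c) × √(120 − 3), the rejection rate is about Φ(z − 1.96) + Φ(−z − 1.96).

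| r | t_PA × t_Y | c | z | rejection |
|---|---|---|---|---|
| 0 | any | 0 | 0 | 5% |
| 0.1 | 0.6 × 0.6 | 0.036 | 0.39 | 7% |
| 0.1 | 0.8 × 0.8 | 0.064 | 0.69 | 11% |
| 0.2 | 0.6 × 0.6 | 0.072 | 0.78 | 12% |
| 0.2 | 0.8 × 0.8 | 0.128 | 1.39 | 28% |
| 0.3 | 0.6 × 0.6 | 0.108 | 1.17 | 22% |
| 0.3 | 0.8 × 0.8 | 0.192 | 2.10 | 56% |

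**Simulation with all three named predictors.** With N = 120 and within-person correlations of 0.6 to 0.8, PA amount was significant in about 5% of trials at r = 0, 7–9% at 0.1, 12–24% at 0.2 and 20–50% at 0.3. The upper ends are a little below the one-predictor approximation. A second simulation with weaker PA tracking (0.5 to 0.7; 2,000 runs per setting) gave 4–5.5%, 6–9%, 9–21% and 15–43%.

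**SB change.** A change score cancels part of the stable level. With the same within-person correlation t for SB and for the outcome, its correlation with the follow-up outcome has size r × t × √((1 − t)/2). At t = 0.8 and r = 0.3 this is 0.3 × 0.8 × √0.1 = 0.076, so z = 0.82 and rejection is about 13%. Simulation of this predictor alone gave 5.6%, 8.8% and 13.1% at r = 0.1, 0.2 and 0.3. In the three-predictor model it was 9–16% at r = 0.2 to 0.3.

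**Which added term does the work.** Rejection for PA amount in the second simulation:

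| Setting | As listed | Plus arm | Plus baseline outcome | Plus both |
|---|---|---|---|---|
| r = 0.2, t_PA 0.7, t_Y 0.8 | 20.6% | 20.9% | 4.8% | 5.0% |
| r = 0.3, t_PA 0.7, t_Y 0.8 | 42.6% | 44.0% | 5.2% | 5.2% |
| r = 0, effect of intervention arms of 0.3–0.5 SD not through PA | 6.2–8.5% | 4.4–4.6% | 8.2–12.4% | 4.0–4.9% |

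The baseline outcome removes the carry-over of pre-existing differences; arm does not. Arm matters only in the last row, where assignment affects the outcome by another route.

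**The case against.** **Silence is not exclusion.** The bracket lists factors to examine and need not be the whole model. This stands. A reader might infer that the plan deliberately leaves out baseline and arm, but the text shows only that it specifies neither. Because the covariate rule stops at the primary analyses, the analyst would have to add the baseline outcome unprompted.

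**The inflation is conditional.** A reader might infer that the regressions are bound to report spurious predictors. The documents do not support that: at r = 0 with no other arm effect, the rate is nominal. The plan also does not say when PA amount is measured, which bears on how strongly it carries the baseline level.

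**The plan speaks of prediction, not cause.** In the simulated setting PA amount does predict the outcome, through baseline. The rejections are errors only if read as effects of behaviour. This is fair, and it is why the results should be labelled as associations. It does not help a reader who wants to know which behaviour to target.

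**Arm adjustment is not free.** It takes out the behaviour variation created by randomisation, costs precision for MedDiet Score, and changes the question to association within arm. This stands, so arm belongs in a sensitivity analysis.

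**Nothing confirmatory depends on this.** Correct. The added value of diet is tested by randomised comparison in Hypotheses 2.1 and 2.2.

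**Conclusion.** The point holds as a minor one. The regressions use follow-up levels, do not specify the baseline outcome, and are not covered by the plan's covariate rule. If baseline behaviour and outcome are correlated, pre-existing differences can pass for behavioural predictors: for PA amount, from almost no inflation at r = 0.1 up to as much as half of trials at r = 0.3 with strong tracking. SB change is affected less. All these sizes rest on assumed correlations.

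A reader might also infer that leaving out arm causes the same bias. It does not: arm alone left the rate unchanged (20.6% against 20.9%). Its omission is a separate matter, mainly for MedDiet Score, for which no separate size is given here.

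**What to change.** Add one sentence to Section 5.1: each of these regressions includes the baseline value of its outcome, and results are reported as associations with confidence intervals, not as effects of PA, SB or diet. State when PA amount is measured.

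The cost is one degree of freedom per model: residual degrees of freedom go from 120 − 4 = 116 to 115. Section 5.1 already schedules cognition and cardiovascular risk factors at baseline. Precision should improve: with a within-person correlation of 0.6 to 0.8, residual variance falls to about 1 − 0.6² = 0.64 or 1 − 0.8² = 0.36 of its former size.

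As a sensitivity analysis, refit with randomised arm (two further degrees of freedom, leaving 113), and say that those coefficients describe association within arm and that MedDiet Score is estimated less precisely. Baseline adjustment removes only differences visible in the measured baseline value, so the associational wording is needed in both versions.
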